9.3.2 Exclusion Criteria

Subjects who meet any of the following criteria will be excluded from this study:

1. Other malignancy active within the previous 2 years except for basal or squamous cell skin cancer, stage 1 prostate cancer, superficial bladder cancer, or carcinoma in situ of the cervix or breast that has completed curative therapy.
2. Current evidence of corneal disorder/keratopathy including but not limited to corneal epithelial thinning, bullous/band keratopathy, corneal abrasion, inflammation/ulceration, or keratoconjunctivitis (to be confirmed by ophthalmological examination). Pre-existing cataract is not a reason for exclusion.
3. Brain or subdural metastases are not eligible, unless they have completed local therapy and have discontinued the use of corticosteroids for this indication for at least 4 weeks before starting treatment in this study. Any signs (eg, radiologic) or symptoms of brain metastases must be stable for at least 4 weeks before starting study treatment.
4. Genetic diseases of the liver that may complicate review of safety data.
5. Known human immunodeficiency virus infection.
6. Uncontrolled significant active infections, except HBV or HCV. Subjects with HBV are eligible, but should be taking appropriate antiviral medication if indicated. Subjects with HCV are eligible but must not be taking any concomitant treatment for HCV while receiving H3B-6527.
7. Major surgery or other locoregional treatment within 4 weeks before the first dose of study drug or radionuclide treatment (eg, ⁹⁰Yttrium intra-arterial treatment) within 8 weeks before the first dose of drug administration.
8. Inability to take oral medication, or presence of malabsorption syndrome or any other uncontrolled gastrointestinal condition (eg, nausea, diarrhea, or vomiting) that might impair the bioavailability of H3B-6527. Subjects with prior gastric resection are eligible.
9. Use of any drug that is a strong inhibitor or inducer of the CYP3A4 enzyme or the P-glycoprotein transporter within at least 2 weeks before the start of study drug and during the conduct of the study unless there is an emergent or life-threatening medical condition that requires it.
10. Use of any drug known to prolong corrected QT (QTc) interval within at least 2 weeks before the start of the study drug and during the conduct of the study.
11. Treatment with proton pump inhibitors that cannot be discontinued 3 days prior to the start of study drug and during the course of the study; antacids are permitted except for calcium carbonate antacids (eg, Tums[®]).
12. Use of other investigational drugs within 28 days or at least 5 half-lives (whichever is shorter) before study drug administration.
13. Previous treatment with a selective FGF19-FGFR4 targeted therapy.

14. Use of any live vaccines against infectious diseases (eg, influenza, varicella) within 4 weeks (28 days) of initiation of study therapy.
15. Presence of gastric or esophageal varices requiring active treatment.
16. A clinically significant electrocardiogram (ECG) abnormality, including a marked baseline prolonged QTc interval (eg, a repeated demonstration of a QTc interval >450 ms).
17. Significant cardiovascular impairment: history of congestive heart failure greater than New York Heart Association Class II, uncontrolled arterial hypertension, unstable angina, myocardial infarction, or stroke within 6 months of the first dose of study drug; or cardiac arrhythmia requiring medical treatment (including oral anticoagulation).
18. Any other major illness, medical condition, or concomitant medication that, in the Investigator's judgment, will substantially increase the risk associated with the subject's participation in this study or would compromise the subject's ability to safely complete the study.
19. Males who have not had a successful vasectomy (confirmed azoospermia) or they and their female partners do not meet the criteria above (ie, not of childbearing potential or practicing highly effective contraception throughout the study period or for 90 days after study drug discontinuation). No sperm donation is allowed during the study period or for 90 days after study drug discontinuation
20. Hypersensitivity to the study drug or to any of the excipients.
21. Intolerance or hypersensitivity to both CT and MRI contrast material that would preclude the ability to acquire the triphasic liver imaging required by the protocol.
22. Inorganic phosphorus > ULN for the institution. Note: Subjects may be on treatment for hyperphosphatemia, but the levels must be normal at screening to participate in this study. Subjects with high levels on screening may subsequently be treated and rescreened and, should they have stable levels for 2 weeks prior to study, may enter the study.
23. Total or ionized serum calcium > ULN for the institution. Note: Subjects may be on treatment for hypercalcemia, but the levels must be normal at screening to participate in this study. Subjects with high levels on screening may subsequently be treated and rescreened and, should they have stable levels for 2 weeks prior to study, may enter the study.
24. Endocrine changes that may result in increases in calcium or phosphate, including, but not limited to, hyperparathyroidism and tumoral calcinosis.
25. Past medical history and/or current evidence of tumoral calcinosis or tissue calcification.
26. Use of calcium or vitamin D supplements or systemic corticosteroids. The duration between the last systemic corticosteroid administration and the first dose of study drug should be at least 2 weeks.
27. Hereditary problems of galactose intolerance, the Lapp lactase deficiency, or glucose-galactose malabsorption.

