9.4.8.1 Prohibited Concomitant Therapy and Procedures

The following therapies and procedures are prohibited during study participation:

- Other investigational drugs.
- Other antitumor therapies such as chemotherapy, surgical resection, or antitumor immunotherapy.
- Proton pump inhibitors.
- Radiotherapy for central metastases (eg, vertebral, mediastinal) will not be allowed; the need for such radiotherapy while on study will be seen as an indication of disease progression and the subject should be withdrawn from therapy. However, palliative radiotherapy for up to 2 local peripheral metastases not being used as target lesions is allowed but the need for such therapy may be an indication of PD and should be discussed with the Sponsor prior to implementation.
- Drugs that are strong inhibitors or inducers of CYP3A4 enzyme (see list in Table 4) or P-glycoprotein transporter.
- Drugs that raise serum calcium and phosphorus levels (eg, vitamin D supplements, calcium dietary supplements, calcium antacids) or systemic corticosteroids. The duration between the last systemic corticosteroid administration and the first dose of study drug should be at least 2 weeks. If a short-term course of systemic corticosteroids is required while on treatment, then study drug must be held while the subject receives systemic corticosteroid treatment. If the subject has not progressed in the interim, resumption of treatment with H3B-6527 may be considered following discontinuation of steroid treatment and a 2-week washout period.

Table 4 Inducers and Strong Inhibitors of CYP3A4

INDUCERS
Carbamazepine, efavirenz, nevirapine, phenobarbital, phenytoin, pioglitazone, rifabutin, rifampin, St. John's Wort, troglitazone
STRONG INHIBITORS
Indinavir, nelfinavir, ritonavir, clarithromycin, itraconazole, ketoconazole, nefazodone

Source: [Indiana University Department of Medicine. <http://medicine.iupui.edu/clinpharm/ddis/clinical-table>](http://medicine.iupui.edu/clinpharm/ddis/clinical-table) Accessed September 7, 2016

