9.4.8.2 Permitted Concomitant Therapy and Procedures

Medications and treatments other than those specified in [Section 9.4.8.1](#), including palliative and supportive care for disease-related symptoms, are permitted during the study. Subjects should be closely monitored, and treatment is to be instituted for disease-related symptoms, as appropriate.

- Growth Factors: Subjects receiving recombinant erythropoietin or darbepoietin- α prior to study start may continue to receive pretreatment doses. Following initiation of study treatment, the use of erythropoietic and granulocyte growth factors is permitted in accordance with local practice or guidelines. American Society for Clinical Oncology guidelines may be implemented at the discretion of the treating physician.
- Management of diarrhea: Subjects should be instructed to take loperamide, 4 mg, at the occurrence of the first loose stool and then 2 mg every 2 hours until they are diarrhea-free for at least 12 hours. During the night, subjects may take 4 mg of loperamide every 4 hours. Subjects should be advised to avoid dehydration through adequate fluid intake. Bile acid sequestrants may be utilized in the case of bile acid diarrhea.

Medications for the treatment of AEs or cancer symptoms, eg, packed red blood cells and pain medications, are allowed. Additionally, medications (not addressed above) used to treat underlying medical conditions at study entry including antiemetics and antidiarrheals will be allowed to continue.

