9.5.5 Completion/Discontinuation of Subjects

The investigator may discontinue study drug for a subject at any time for safety or administrative reasons. A subject may elect to discontinue study drug and study participation at any time for any reason. All subjects who discontinue study drug are to complete the Off-Treatment visit, as indicated in the Schedule of Procedures/Assessments [Table 6](#) and [Table 7](#).

Study drug is to be discontinued for the following reasons:

- Progression of disease that, in the opinion of the investigator, precludes further study treatment. (After consultation with the Sponsor, H3B-6527 may be continued for a subject who has met the criteria for PD but, in the investigator's opinion, is receiving benefit.)
- Occurrence of an unacceptable AE.
- Subjects who do not receive study drug for at least 17 of 21 days (approximately 80%, not necessarily consecutively) during the first cycle for reasons not considered to be a DLT by both the investigators and the Sponsor will be replaced. The subjects who are replaced will not be considered evaluable for DLT assessments.
- Subject requires use of a prohibited concomitant medication or therapy.
- General or specific changes in the subject's condition unacceptable for further treatment within the study parameters, in the judgment of the investigator.
- Non-compliance.
- Lost to follow-up.
- Subject, investigator, or Sponsor request.

The reason for study drug discontinuation is to be documented in the CRF.

Subjects who discontinue study drug for reasons other than PD are to continue to have tumor measurements and disease response assessments performed every 6 weeks until the development of PD. After development of PD, subjects who discontinue study treatment, regardless of their reasons for doing so, will be followed for survival approximately every 12 weeks for up to 12 months or until 6 cycles after last patient in, death, loss to follow-up, or withdrawal of consent, whichever occurs first. However, subjects may continue to receive study treatment, as long as they demonstrate clinical benefit as judged by the investigator after discussion with the Sponsor or until the end of the study.

Study participation also may be discontinued for any of the following reasons:

- Subject withdrawal of consent
- Non-compliance
- Lost to follow-up
- Sponsor request
- Closure of the study by the Sponsor.

The reason for study discontinuation is to be documented in the CRF.

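### The protocol contradicts itself on which drugs are barred after first dose: exclusion criteria 6, 9 and 10 do not match sections 9.4.8.1, 9.4.8.2 and 9.5.5

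*Protocol*

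**What the plan says.** Three eligibility criteria in Protocol 9.3.2, repeated in the synopsis, extend beyond enrolment.

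- Criterion 10 rules out medicines "known to prolong corrected QT (QTc) interval within at least 2 weeks before the start of the study drug and during the conduct" (that is, throughout the trial). It carries no exception.
- Criterion 6 admits subjects with hepatitis C, but they "must not be taking any concomitant treatment for HCV while receiving H3B-6527".
- Criterion 9 bars strong CYP3A4 or P-glycoprotein inhibitors or inducers for at least 2 weeks before dosing and "during the conduct of the study unless there is an emergent or life-threatening medical condition that requires it".

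The sections that govern treatment after dosing read differently.

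- Section 9.4.8.1 opens with "The following therapies and procedures are prohibited during study participation" and gives six bullets: investigational drugs; other antitumor therapy; proton pump inhibitors; radiotherapy to central metastases; strong CYP3A4 or P-glycoprotein inhibitors or inducers; and drugs that raise calcium or phosphorus, together with systemic corticosteroids. QT-prolonging drugs and hepatitis C treatment do not appear. The CYP3A4/P-glycoprotein bullet has no exception.
- Section 9.4.8.2 says that treatments outside the 9.4.8.1 list, "including palliative and supportive care for disease-related symptoms, are permitted during the study".
- Section 9.5.5 gives this among the reasons for which study drug is to be discontinued: "Subject requires use of a prohibited concomitant medication or therapy".
- For a short steroid course, 9.4.8.1 has its own rule: "study drug must be held while the subject receives systemic corticosteroid treatment", with possible resumption after a 2-week washout.

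**The concern.** Once a subject is dosed, site staff consult the concomitant-therapy and discontinuation sections more readily than the eligibility list. For three drug classes the two sources disagree, so the answer depends on which page is open.

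Two things are at stake. The first is safety: a restriction on QT-prolonging drugs that is meant to last through treatment is missing from the list that would enforce it. The second is interpretation. Changes in ECG parameters belong to the primary safety endpoint (Protocol 9.7.1.1, SAP 5.1.1). Criterion 10 gives a baseline free of QT-prolonging drugs. If one is started later, any QTcF rise it causes is recorded as change from baseline on H3B-6527, and there is no control arm against which to judge it. SAP 5.6.5 counts every subject with at least one abnormal post-baseline QTcF and makes no provision for co-medication.

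For criterion 9 the stake is uniform handling. Two sites could continue or discontinue the same kind of subject, which would alter exposure and the discontinuation tables.

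**Working it through.** The plan states no figure for this point, so the check is mainly a comparison of text.

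**Step 1. Passages side by side**

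| Drug class | 9.3.2 | 9.4.8.1 | 9.4.8.2 | 9.5.5 | Result |
|---|---|---|---|---|---|
| QT-prolonging drugs | Barred on study (criterion 10) | Not listed | Permitted by default | Unclear whether it counts as prohibited | Barred and permitted |
| Hepatitis C treatment | Barred on study drug (criterion 6) | Not listed | Permitted by default | Unclear, as above | Barred and permitted |
| Strong CYP3A4/P-gp inhibitors or inducers | Barred, with emergency exception (criterion 9) | Listed, no exception | Not applicable | Discontinue | Allowed in an emergency, or prohibited and discontinued |
| Systemic corticosteroids | Barred at entry (criterion 26) | Listed, with hold and possible resumption | Not applicable | Discontinue; no cross-reference | Missing cross-reference |

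Only criterion 9 conflicts directly with 9.5.5. For criteria 6 and 10 the conflict is with 9.4.8.2. Section 9.5.5 is merely ambiguous there, because its word prohibited may or may not reach beyond the 9.4.8.1 list.

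**Step 2. The synopsis.** Its prohibited list has the same two omissions and the same unqualified CYP3A4/P-glycoprotein bullet against criterion 9. It does not contain the general permission found in 9.4.8.2.

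**Step 3. Other text.** Apart from the eligibility criteria and the amendment log, no current passage bars QT-prolonging drugs on study.

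**Step 4. Where QTc is read.** Holter recordings are taken on Cycle 1 Days 1 and 8 in Part 1 (Protocol 9.5.1.4.6). Single 12-lead ECGs are scheduled on Day 1 of each cycle in both parts (Tables 6 and 7). The QTcF categories in SAP 5.6.5 (above 450, 480 and 500 ms; increases above 30 and 60 ms) cover both parts.

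**Step 5. What one affected subject would weigh.** This is 1/n and illustrates scale only; it does not estimate how often the event would occur.

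- Cohort of 3: 1/3 = 33%. Cohort of 6: 1/6 = 17%.
- Dose level expanded to 12 evaluable subjects (Table 1 note): 1/12 = 8%.
- Expansion arm of 40: 1/40 = 2.5%.
- All of Part 1, 30 to 48 subjects: 1/30 = 3.3% to 1/48 = 2.1%.

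**Step 6. Criterion 9 in Cycle 1 of Part 1.** Suppose the need arises on Day d and study drug stops that day. The subject has d − 1 dosing days, which is below 17 whenever d ≤ 17. If the drug is continued instead, the subject can reach 21. The passage followed can therefore decide whether the subject meets the 17-of-21-day requirement for DLT evaluability.

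**The case against.** **Criterion 10 still stands.** It is specific, and Protocol 11.2 requires strict adherence. A general residual clause does not plainly override a specific bar. This is right. A reader might infer that QT-prolonging drugs are simply allowed after dosing, but the documents do not support that: they say both things. What remains is the contradiction.

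**Co-medication can be traced.** All medications from consent onward go on the CRF (9.4.8) and are listed. ECG abnormalities are listed by subject. A QTcF above 450 ms with a rise above 60 ms is to be treated as an AE (9.5.1.4.1), AEs receive a causality assessment, and the Safety Review Committee reviews all available safety data. These points stand and limit the harm to interpretation. They do not close the safety gap, and the outlier tables would still count the subject without qualification.

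**The steroid rule reads naturally as a specific exception to the 9.5.5 bullet.** Accepted, so only a cross-reference is missing. A reader might also infer that hold versus discontinue changes the 17-of-21-day count. It does not. For a course starting on Day d, discontinuing leaves d − 1 dosing days. Holding for at least 1 steroid day plus 14 washout days leaves 6 when d ≤ 7 and d − 1 after that. Under both readings 17 is reached only when d ≥ 18. Nor does the washout always take 14 days of Cycle 1: that requires the course to end by Day 7, since later washouts run into Cycle 2.

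**The 1/n percentages are not evidence of bias.** Correct. They would apply to any single event, and the documents give no frequency for QT-prolonging co-medication.

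**Conclusion.** The contradictions for criteria 6, 9 and 10 are in the current text and should be corrected. They concern operative rules on what a treated subject may receive, and one bears on ECG change within a primary endpoint of an uncontrolled trial.

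The size of any effect on QTcF cannot be stated. It depends on how often sites would act on 9.4.8.2 rather than criterion 10 and on which drugs they would use, and the documents give neither. The direction is upward if it occurs, assuming that the added drug prolongs QTc and that the baseline was free of such drugs. The hepatitis C conflict has the same form, but no specific analytic consequence is shown for it. The steroid point is minor.

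A reader might infer that the synopsis repeats the whole conflict. It repeats the omissions and the criterion 9 conflict, but not the blanket permission, so its prohibited list is incomplete rather than permissive.

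**What to change.** Reconcile criteria 6, 9 and 10, sections 9.4.8.1, 9.4.8.2 and 9.5.5, and the synopsis, so that all carry:

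- one list of drugs barred after first dose;
- one statement on whether the emergency exception for CYP3A4/P-glycoprotein drugs applies;
- one stated consequence for each drug class, with 9.5.5 cross-referring to the steroid rule in 9.4.8.1.

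Which version stands is for the sponsor to decide. The cost is amendment wording, and no new data are needed.

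Optionally, SAP 5.6.5 could flag QTcF outliers recorded while a QT-prolonging drug was in use, taken from the concomitant medication CRF. Neither document defines which drugs count, so the sponsor would need to specify a reference list and apply it to the coded medications. That is a small amount of added analysis work.

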9.4 Treatments

9.4.1 Treatments Administered

All subjects will receive H3B-6527 at their assigned dose daily PO. For the purposes of this study, a cycle length is defined as 21 days.

9.4.2 Guidelines for Continuation of Treatment

Study drug should continue to be administered as planned unless a DLT has occurred. Subjects who experience a DLT during C1 will be discontinued from treatment. In rare cases, an exemption to study discontinuation for a DLT in 1st cycle may be considered after discussion between the treating physician, Sponsor and study medical monitor. If a subject should experience a DLT or DME (ie, an AE meeting the criteria for a DLT but occurring after C1) during the study then study treatment will be interrupted and subjects may, at the discretion of the investigator, and after discussion with the Sponsor, be allowed to continue study drug at a reduced dose, if the following criteria are met:

- ANC $\geq 1.0 \times 10^9/L$ (1,000/mm³)
- Platelet count $\geq 75 \times 10^9/L$ (75,000/mm³)
- All other nonhematologic treatment-related toxicities are Grade 0 or 1 (except alopecia) or return to baseline level
- Clinical benefit is being received, and
- Evidence of an otherwise favorable risk/benefit profile.

The magnitude of the dose reduction cannot be specified *a priori* since the actual doses evaluated and the dose-toxicity relationship will not be known until there is clinical experience with H3B-6527; however, a minimum reduction of 33% must be taken. The dose chosen will require discussion and agreement between the investigator and Sponsor following review of the relevant clinical data.

Dose reductions are allowed for all subjects. However, once the H3B-6527 dose has been reduced for a given subject, no re-escalation will be permitted for that subject.

A maximum of 2 dose reductions will be allowed as needed, but study treatment should not be resumed in the case of the following treatment-related events:

- Occurrence of a DLT in C1 except upon agreement with investigator, Sponsor and medical monitor. A dose reduction must be taken if treatment is resumed.
- CTCAE Grade 3 or 4 cardiac event
- Nonhematologic events of Grade 4 severity
- Dose delay of ≥ 21 days for a treatment-related event in C2 and beyond.

9.4.3 Identity of Investigational Product

H3B-6527 drug product for clinical studies is supplied as Swedish orange, opaque, hypromellose shell capsules, size 4 containing 50 mg, size 2 containing 100 mg, or size 0 containing 200 mg of H3B-6527 drug substance. The composition ratio of the capsule content is the same for the 3 strengths.

H3B-6527 capsules (28) are packaged in a 50-mL high-density polyethylene bottle with 2 g of desiccant and closed with a polypropylene screw cap.

9.4.3.1 Chemical Name, Structural Formula of H3B-6527

Test drug code: H3B-6527

[figure not shown]
Generic name: Not assigned

Chemical name: N-(2-((6-(3-(2,6-dichloro-3,5-dimethoxyphenyl)-1-methylureido)pyrimidin-4-yl)amino)-5-(4-ethylpiperazin-1-yl)phenyl)acrylamide

Molecular formula: C₂₉H₃₄Cl₂N₈O₄

Molecular weight: 629.54

Structural formula: The structural formula is as follows:

Chemical Formula: C₂₉H₃₄Cl₂N₈O₄
Molecular Weight: 629.54

